7.4 Medical Device Reporting (MDR)

If an adverse event occurs that is directly caused by a marketed product used in the study, the adverse event should be reported immediately, but in any case within 24 hours, to the Customer Service Department [REDACTED] Also contact the Ascensia Diabetes Care representative listed in Section 12.0.

8.0 STUDY TERMINATION CRITERIA

Criteria to Withdraw Subject from Study

Subjects may be withdrawn from the study at their own request for any reason at any time.

Subjects may be withdrawn at the discretion of the Investigator for one of the following reasons:

- Adverse Event
- Subject non-compliance with protocol requirements

- Other, at the discretion of the investigator

Data collected from withdrawn subjects will be analyzed as appropriate and results retained for safety assessments.

Data will not be retained in analyses related to the primary objective of the study if there is a valid reason to believe that the data may be biased, incorrect or confounded.

9.0 REGULATORY

Regulatory Status of the System

The Contour Next One meter and Contour Diabetes App 1.0 (which is a simpler version of this App) have CE-mark, but may still be investigational in the US. The Contour Diabetes App 2.0 which is the focus of this study will be investigational at the time of the study. In addition to the regulations outlined in the Ascensia Diabetes Care Global Clinical Affairs standard operating procedures, this protocol also complies with the clinical trial regulations of British Standard BS EN 13612:2002, and “Performance evaluation of in vitro diagnostic medical devices”, GCP ISO 14155.

Institutional Review Board Approval

An Institutional Review Board (IRB) must approve this protocol, the Informed Consent (IC) document and any other supporting study documents which impact subject safety, prior to study initiation. The investigational site may not begin the study until the IRB has given its written and dated approval via a letter that identifies the version/date of the protocol and Informed Consent Form (ICF). A copy of the approval letter and the approved ICF must be provided to the Investigator and to Ascensia Diabetes Care prior to the Study Initiation Visit.

Informed Consent Requirement

Each subject must provide informed consent before she/he can participate in the study. The informed consent process fully appraises the subjects of the risks and benefits to them and to society for participating in the study. The ICF will clearly state that designated study personnel will be able to view the subject’s medical information. The ICF will also state that Ascensia Diabetes Care representatives may observe some subjects as part of study staff training, study monitoring or for troubleshooting problems with the investigational devices. If the subject understands and agrees to participate in the study, he/she will sign the ICF and then it will be signed by the person conducting the informed consent process. All subjects will be given a copy of the ICF. If a subject has a question about his/her rights, he/she may contact a member of the IRB at any time during or after study participation.

Study Documentation and Procedures

The investigator will keep study records for a minimum of three years. If the investigator is unable to store the documents for the required time, other arrangements may be made with Ascensia Diabetes Care.

Investigational Devices

The investigational Contour Diabetes App 2.0 will be un-installed from the subjects’ mobile device at Visit 2, after the subject has completed the study. The Contour Next One meters, UGs and QRGs are for investigational use only and must be accounted for and returned to Ascensia. [name], Study Manager, is responsible for oversight of tracking of investigational materials. All

meters should be disinfected per Appendix B prior to shipping back to Ascensia Diabetes Care.

Study Monitoring

The study will be monitored by Ascensia Diabetes Care personnel or designee(s). A monitoring plan will be completed by the Study Manager/Study Monitor prior to the study. The study monitor or designee will conduct a study initiation visit, at least 1 monitoring visit, and a close out visit. (Note: the latter two visits may occur within a continuous timeframe).

Ascensia Diabetes Care representatives or a designee may observe some subject visits as part of study staff training, study monitoring or for troubleshooting problems with the investigational devices. Ascensia Diabetes Care representatives will maintain subject confidentiality and will not interfere with the rights of human subjects or with their safety or bias study conduct.

Site staff will correspond with Study Manager daily during the enrollment phase, reporting the status of subject enrollment, by providing subject ID and subject study email address (de-identified) so the Ascensia Diabetes Care administrator can verify the setup profile was initiated successfully.

Investigator's Report of Study Closure

The Ascensia Diabetes Care Study Manager or designee will send a letter to the site informing them that the study is closed. The study will be considered closed when the data has been locked for data analysis.

The Investigator or designee will submit a report summarizing subject disposition and other study details, as appropriate, to the Ascensia Diabetes Care Study Manager and the reviewing IRB/EC. This report will be completed within 3 months of the study closure date.

In addition, the Ascensia Diabetes Care Study Manager or designee will report the completion of the study to the IRB within 6 months of study closure.

Registration of Trial

The trial will be registered with clinicaltrials.gov as required.

10.0 DATA COLLECTION AND MANAGEMENT

A unique number will identify each subject. The unique number will be the only identifying information entered. A master list of subject names, with their subject IDs, will be kept by the Investigator at the study site. The Investigator will retain all signed IC documents.

Study data will be recorded on paper forms that will serve as source documents. These data will be entered by the site staff (or designee) into an Electronic Data Capture (EDC) system provided by Ascensia Diabetes Care. In addition to data collection, the EDC system will be used for data cleaning as well as monitoring operations. Site and sponsor users will be trained on the system prior to the study start at their site, and their access to EDC system will be contingent upon successful completion of training requirements. Study personnel will complete and sign all appropriate source document forms in compliance with Good Clinical Practice (GCP). Source documents (Forms) should be completed legibly, in black or blue ink. If it is necessary to make corrections, a single line should be drawn through the original entry, the new entry written in, and the correction initialed and dated by the individual making the correction.

The original forms will be retained by the Investigator for a minimum of three years.

The Investigator or designee will sign and date an Adverse Event Form for each Adverse Event experienced by any subject.

Data Downloaded from the Cloud

Additionally, apart from the data collected, then entered into EDC, de-identified data collected in the Contour Diabetes App will be uploaded to the Cloud throughout the study into a US server (US site data). At the end of the study the cloud data will be downloaded to an Ascensia Diabetes Care database. This downloaded cloud data will be able to be accessed by Ascensia Diabetes Care engineering group and Ascensia Diabetes Care Global Medical/Clinical Affairs personnel. Summaries of the cloud data will be included in the Final Clinical Study Report and Statistics Reports. The downloaded data will include the following information, all of which are anonymous, de-identified subject data:

- Subject study email address
- Meter serial number
- Meter and manually entered blood glucose readings with associated dates, times and meal markers
- Settings: target ranges, low, high, and critical lows and highs
- Entries such as notes, exercise (type and duration), food
- Smart Reminders – record of reminders set by the subject
- Record of pattern notifications including pattern type, dates, times, and pattern status indicators.

The following will not be saved and included in the study database: subject emergency contact name, phone number or any other identifying information.

11.0 STATISTICAL METHODS AND ANALYSIS

An $n = 40$ responses yields approximately a 93.3% chance of “passing” the primary objective criteria if there is an 85% probability that a randomly selected person could perform the critical tasks successfully.

Performance Criteria for subject’s success at utilizing system features:

There is at least an 85% probability that any user would be able to utilize the App features with success. A hypothesis test will be performed to test the hypotheses for each feature individually:

$$H_0 : \Pr\{user\ can\ perform\ a\ given\ basic\ task\ successfully\} < 85\%$$

against:

$$H_1 : \Pr\{user\ can\ perform\ a\ given\ basic\ task\ successfully\} \geq 85\%$$

With $n = 40$ responses, we must observe at least 31 responses with a 1, 2, or 3 score on a critical questionnaire statement (statements 1, 8, 9, and 42 as shown in Appendix A) to reject the null hypothesis, H_0 . This criterion yields the following risk characteristics:

There is approximately a 93.3% chance (power) of obtaining at least 31 “successes” out of $n = 40$ responses IF the actual probability of success is 85%. Conversely, there is approximately a 90% chance of failing to obtain at least 31 successes out of $n = 40$ responses IF the actual probability of success is only about 66.8%.

It is likely that the actual sample size will not be exactly 40, but in fact may be slightly higher or lower. Responses of “no opinion” will not be counted for any hypothesis test. The critical values for hypothesis tests will be adjusted for sample size, to maintain approximately the same power characteristics, i.e., the probability of rejecting the null if the success probability is 85% will be kept to be no greater than 95%.

The results accessing each feature will be evaluated independently. Statements 1, 8, 9, and 42 in Appendix A correspond to the primary endpoint and the 85% criterion.

Cluster Analyses and Other Associated Analyses

Ordinal-scaled variables from ease of use and diabetes management attitude surveys will be used in a k-means cluster analysis, to assess the possibility of unknown groupings (clusters) of subjects within the study sample. Other variables, such as diabetes type, age, gender, and frequency of blood glucose testing will be used to potentially further characterize the groupings. Inasmuch as there is no a priori expectation for the numbers of clusters, nor is there any expectation or hypotheses that any variables will have associations with clusters, these analyses should be considered exploratory.

A condition of hardware/software failure that cause or contribute to a subject's inability to access or utilize any given feature will be considered an un-evaluable observation. (i.e., will not be included in the numerator/denominator for calculating percentage of user success.)

Frequency distributions of scores will be provided for the other variables, i.e., subjects' ratings on ease of use and subjects' ratings on clarity/utility of user instructions, subjects' opinions about their use of the Contour Diabetes App 2.0 system. Correlation coefficient, and associated 95% two-sided confidence interval, will be computed for laboratory HbA1c versus average glucose. Average glucose will be computed from cloud data.

Histograms for the change in HbA1c, fructosamine, weight, and total daily insulin (as reported by subjects) from visit 1 to visit 2 will be constructed. ANOVA (or equivalent method) will be used to determine whether change in HbA1c, Fructosamine, weight, and total daily insulin are significantly different from zero. P-values less than or equal to 0.05 will be considered significant. Confidence intervals (95%, two-sided) for the average change in HbA1c, fructosamine, weight, and total daily insulin dose will be computed.

Average daily utilization rates for selected App features will be computed, together with 95% (non-simultaneous) confidence intervals. Frequency tables for discrete demographic variables will be constructed. Descriptive statistics, such as mean, standard deviation, median, minimum, maximum will be computed for continuously-valued demographic variables (e.g., subject age).

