Questionnaire outcome – Subjects will complete a questionnaire at the end of the study at Visit 2 that will assess the usability of the App 2.0 with the meter and their experience using the Contour Diabetes App 2.0 system in their daily diabetes management routine. The App features will be evaluated independently by asking a series of questions about each. The features evaluated may include:

- Obtain a synced blood glucose reading
- Recognize and use “Smart Reminders”
- Access and interpret glucose displays such as Expanded Graph and My Readings views.
- Recognize glucose pattern notifications (as applicable since all subjects may not receive pattern messages)

Goal: For the following features, at least eighty five percent (85%) of potential users should be able to report that they were able to successfully utilize the feature. A rating of 1, 2, or 3 for each feature (1=strongly agree, 2=agree, 3=neither agree nor disagree, 4=disagree, 5=strongly disagree) indicates that the subject was able to successfully utilize the feature. These include:

- Obtain a synced blood glucose reading
- Recognize and use “Smart Reminders”
- Access and interpret glucose displays such as Expanded Graph and My Readings views.

Statements such as 1, 8, 9, and 42 in Appendix A correspond to statements subject to the 85% criterion. These statements are shaded.

Secondary Endpoints

- A change from baseline to completion of:
 - HbA1c
 - Fructosamine
 - Weight
 - BMI
 - Total Daily Insulin (self-reported bolus and basal doses)
- Feature Utilization rates

Safety

The following are to be captured:

- Adverse events
- Severe Hypoglycemic episodes
- Hospitalizations

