Appendix A – Contour Diabetes App 2.0 Questionnaire

Obtain a synced blood glucose reading

1. Overall, I was able to successfully sync my blood glucose value on the meter with the App.

1= Strongly Agree

2= Agree

3= Neither Agree nor Disagree

4= Disagree

5= Strongly Disagree

No opinion

2. Overall, I am satisfied with how easily my blood glucose value on the meter syncs with the App.

1= Strongly Agree

2= Agree

3= Neither Agree nor Disagree

4= Disagree

5= Strongly Disagree

No opinion

3. The syncing of my blood glucose value from the meter to the App is reliable.

1= Strongly Agree

2= Agree

3= Neither Agree nor Disagree

4= Disagree

5= Strongly Disagree

No opinion

4. The syncing of my blood glucose value from the meter to the App is accurate.

1= Strongly Agree

2= Agree

3= Neither Agree nor Disagree

4= Disagree

5= Strongly Disagree

No opinion

5. Did you change time zones during the study? Yes or No

6. If Yes, did the App adjust to the time zone change as expected or did you experience any problems? Please comment below.

(open text field)

7. Do you have any comments about syncing of the meter with the App?

(open text field)

Access and interpret glucose displays such as expanded graph and sequential views.

8. Overall, I was able to successfully access glucose displays such as Expanded Graph view and My Readings view in the App.

- 1= Strongly Agree
- 2= Agree
- 3= Neither Agree nor Disagree
- 4= Disagree
- 5= Strongly Disagree
- No opinion

9. Overall, I was able to successfully interpret glucose displays such as Expanded Graph view and My Readings view in the App.

- 1= Strongly Agree
- 2= Agree
- 3= Neither Agree nor Disagree
- 4= Disagree
- 5= Strongly Disagree
- No opinion

10. Accessing the Expanded Graph view was:

- 1= Very Simple
- 2= Simple
- 3= Neither Simple nor Difficult
- 4= Difficult
- 5= Very Difficult
- No opinion

11. Using the Expanded Graph view was:

- 1= Very Simple
- 2= Simple
- 3= Neither Simple nor Difficult
- 4= Difficult
- 5= Very Difficult
- No opinion

12. Expanded Graph View in the App was understandable and easy to interpret.

- 1= Strongly Agree
- 2= Agree
- 3= Neither Agree nor Disagree
- 4= Disagree
- 5= Strongly Disagree
- No opinion

13. Expanded Graph View in the App was helpful for me in managing my diabetes.

1= Strongly Agree

2= Agree

3= Neither Agree nor Disagree

4= Disagree

5= Strongly Disagree

No opinion

14. Accessing the My Readings view was:

1= Very Simple

2= Simple

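### Is the 93.3% chance of passing in Section 11.0 too high because the displays feature rests on two critical statements?

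*Combined protocol and SAP*

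**What the plan says.** The opening sentence of Section 11.0 (Statistical Methods and Analysis) justifies 40 responses with a figure of 93.3%, given as the probability of meeting "the primary objective criteria if there is an 85% probability that a randomly selected person could perform the critical tasks successfully".

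The rest of the section is more specific:

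- On the unit of testing: "A hypothesis test will be performed to test the hypotheses for each feature individually". The hypotheses that follow concern the probability that a user succeeds at one given task.
- The rejection rule asks for at least 31 of 40 favourable scores "on a critical questionnaire statement (statements 1, 8, 9, and 42 as shown in Appendix A").
- The power statement follows that rule: "There is approximately a 93.3% chance (power) of obtaining at least 31" successes out of 40 if the true probability is 85%.
- For other sample sizes the cutoff is adjusted so that "the probability of rejecting the null if the success probability is 85% will be kept to be no greater than 95" percent.
- The endpoint is then identified: "Statements 1, 8, 9, and 42 in Appendix A correspond to the primary endpoint and the 85% criterion". Results are to be evaluated feature by feature.

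Section 3.0 (Primary Endpoints) names three features under the 85% goal. One of them is "Access and interpret glucose displays such as Expanded Graph and My Readings views". Appendix A covers it with two critical items. Statement 8 reads "Overall, I was able to successfully access glucose displays such as Expanded Graph view and My Readings view in the App"; statement 9 has the same wording with interpret in place of access. Syncing (statement 1) and Smart Reminders (statement 42) have one critical item each.

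**The concern.** The section uses 93.3% in two places that seem to describe different events. In the opening sentence it is the chance of meeting criteria, in the plural, for tasks, in the plural. Later it is the chance that one statement reaches 31 of 40. Four statements carry the primary endpoint, and the displays feature needs two of them if access and interpret are both taken literally. A chance that holds for one statement is generally too high for two that must both pass, so the justification for 40 subjects would look optimistic.

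There is also a gap. The plan promises a test per feature, its rule works per statement, and no sentence says what is concluded about displays if statement 8 passes and statement 9 fails, or the reverse. The fear is that the feature-level conclusion would be chosen after the results are seen.

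**Working it through.** **Inputs.** From Section 11.0: n = 40, cutoff 31, success probability 0.85, lower operating point 66.8%, and a 95% cap on the pass chance at 85%. From Appendix A: two critical statements for displays. The documents give no correlation between a subject's answers, so a range is shown.

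**1. Reproduce the plan's figures (one statement).** With X ~ Binomial(40, p):

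- P(X ≥ 31 | 0.85) = 0.9328, stated as 93.3%.
- 1 − P(X ≥ 31 | 0.668) = 0.9004, stated as about 90%.
- Cutoffs 30 and 32 give 0.9701 and 0.8646 at 85%, so neither matches the stated figure.

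Both stated figures are correct for one statement.

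**2. Add a both-must-pass rule for statements 8 and 9.** This rule is an assumption; the plan does not state it.

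- Independent answers: 0.9328² = 0.8701. Chance that exactly one passes: 2 × 0.9328 × 0.0672 = 0.1254.
- Correlated answers: exact calculation from paired yes/no answers, each with probability 0.85 and within-subject correlation φ. The split chance is 2 × (0.9328 − joint).

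| φ | Both pass | Split |
|---|---|---|
| 0 | 87.0% | 12.5% |
| 0.3 | 87.8% | 11.0% |
| 0.5 | 88.5% | 9.5% |
| 0.7 | 89.6% | 7.4% |
| 0.9 | 91.3% | 4.0% |
| 1 | 93.3% | 0% |

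**3. Vary the true success probability (n = 40, independent answers).**

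| True success | One statement | Both | Split |
|---|---|---|---|
| 80% | 73.2% | 53.5% | 39.3% |
| 85% | 93.3% | 87.0% | 12.5% |
| 90% | 99.5% | 99.0% | 1.0% |
| 95% | over 99.9% | over 99.9% | near 0% |

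**4. Vary the sample size.** Take the smallest cutoff whose pass chance at 85% does not exceed 95%; this gives 31 at n = 40. For n = 40 to 48, one statement passes with 89.9% (n = 43, cutoff 34) to 94.3% (n = 44, cutoff 34). Two independent statements both pass with 80.9% to 89.0%. At n = 38 (cutoff 30) the figures are 89.4% and 80.0%. The cap alone limits two independent statements to 0.95² = 90.3%, so more subjects would not remove the difference.

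**5. Test the opening sentence for consistency.** It has a condition (85% can perform the tasks) and an event (the criteria are passed).

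- Both read per task: the chance is exactly 93.3%.
- Both read jointly: if 85% of people can do all the tasks, the number in the sample who can is Binomial(40, 0.85). It reaches 31 with probability 0.9328, and whenever it does, every statement has at least 31 successes. The joint pass chance is therefore at least 93.3%.
- Condition per task, event joint: only this mixed reading makes 93.3% too high.

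**The case for a change.** The best case for a change is that the opening sentence is the one a reader takes as the sample size justification, and that access and interpret naturally means both. Plausible positive correlation reduces the difference without removing it: even at φ = 0.9 both pass in 91.3%, and a split occurs in 4.0%. Splits are also not rare if true success is below the goal (39.3% at 80% with independent answers). Statements 8 and 9 can have different denominators, because no-opinion answers and observations spoiled by hardware or software failure are dropped. Settling the split rule beforehand would cost a sentence or two.

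The arithmetic stands, and so does the observation that the split rule is unwritten. The inference to a wrong power figure does not. The 87.0% needs a both-must-pass rule that is not in the plan. It also needs independence between two adjacent items that differ in one verb, share a scale and are answered by the same person at the same visit. The hypothesis wording that makes the 85% condition per task makes the pass event per task as well. The figure for all four statements, 0.9328⁴ = 75.7% under independence, answers a question the plan does not ask, since it evaluates features separately.

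**Conclusion.** The concern does not call for a change. The 93.3% is correct for the test the plan defines: one critical statement, 40 responses, cutoff 31, true success 85%. Section 11.0 says so directly after the rejection rule, and the loose plural in its opening sentence changes no sample size, cutoff, analysis set or result.

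The missing rule for a split between statements 8 and 9 is a gap that analysts fill sensibly. Each statement has its own test, and if one passes and the other fails, both outcomes are reported and the reader sees that users could access the displays but not interpret them, or the reverse. That is more informative than a single pass or fail for the feature.

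If a combined displays claim were made and required both statements, its chance at 85% true success would lie between 87.0% (independent answers) and 93.3% (full agreement), with the correlation unknown. Under independence it would be 99.0% at 90% true success. These figures rest on n = 40 evaluable answers to each statement and equal success probabilities. The four statement-level results are the same under every reading.

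### The primary test states H0 as success below 85% but rejects it at 31 of 40 (77.5%), so a pass does not show that at least 85% of users succeed

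*Combined protocol and SAP*

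**What the plan says.** Section 11.0 gives the performance criterion as follows: "There is at least an 85% probability that any user would be able to utilize the App features with success". For each feature it sets H0: p < 85% against H1: p ≥ 85%, where p is the probability that a user succeeds. With n = 40, "we must observe at least 31 responses with a 1, 2, or 3 score on a critical questionnaire statement" to reject H0.

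Two operating figures follow. The first is "There is approximately a 93.3% chance (power) of obtaining at least 31" successes if p is 85%. The second is that "there is approximately a 90% chance of failing to obtain at least 31 successes" if p is only about 66.8%. The opening sentence of the section uses the first figure differently: 40 "responses yields approximately a 93.3% chance of" passing.

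For other numbers of responses, critical values are to be adjusted "to maintain approximately the same power characteristics", which the plan explains as meaning that "the probability of rejecting the null if the success probability is 85% will be kept to be no greater than 95" per cent.

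The rule applies to statements 1, 8, 9 and 42, which Section 11.0 ties to the primary endpoint. Sections 2.0 and 3.0 set the matching 85% goal for potential users. No alpha and no confidence interval is given for these statements. The 0.05 threshold in Section 11.0 belongs to the changes in HbA1c, fructosamine, weight and insulin dose.

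**The concern.** Rejecting H0: p < 85% is a claim that p is at least 85%. A cut-off for such a claim should normally lie above 85% observed, so that the data exclude lower values with a stated error. Here it lies below, and counts of 31, 32 and 33 out of 40 all reject H0 although the observed rate misses the goal.

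The figure labelled *power* is evaluated where H0 and H1 meet. At that point the probability of rejecting is both the lowest power over H1 and the limit of the type I error over H0. A reader who sees 93.3% power and a rejected H0 would take the 85% criterion as demonstrated, and the rule cannot carry that conclusion. Since it decides every primary statement, the stated primary conclusion is at stake.

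**Working it through.** **Inputs.** All are from Section 11.0 unless noted: n = 40; reject at k = 31 or more; boundary p = 0.85; second operating point p ≈ 0.668; cap of 95% on rejection at p = 0.85. Enrolment is about 48 (Section 4.0), with at least 40 completers (Section 5.1.1).

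**Formula.** With X successes among n responses, P(X ≥ k | n, p) = Σ C(n,x) pˣ (1−p)ⁿ⁻ˣ, summed from x = k to n.

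**1. The plan's own figures reproduce.**
- P(X ≥ 31 | 40, 0.85) = 0.9328; stated 93.3%.
- 1 − P(X ≥ 31 | 40, 0.668) = 1 − 0.0996 = 0.9004; stated about 90%.

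**2. Type I error of the stated test.** P(X ≥ 31 | 40, p) is continuous and increasing in p. It is 0.9048 at p = 0.84, 0.9303 at 0.849 and 0.9328 at 0.85. Its supremum over H0 (p < 0.85) is therefore 0.9328, approached but not attained.

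**3. Rejection inside H0.**

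| True p | P(reject H0), n = 40 |
|---|---|
| 80% | 73.2% |
| 75% | 44.0% |
| 70% | 19.6% |
| 66.8% | 10.0% |

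The probability crosses 50% at p = 76.0%, so between there and 85% a true H0 is rejected more often than not. At p = 80%, the part due to 31 to 33 successes is P(X ≥ 31) − P(X ≥ 34) = 0.7318 − 0.2859 = 0.4459. So 44.6 of the 73.2 percentage points come from observed rates below 85%.

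**4. What an observed count supports (exact Clopper-Pearson).**

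| Observed | One-sided 95% lower bound | Two-sided 95% CI |
|---|---|---|
| 31/40 (77.5%) | 64.0% | 61.5% to 89.2% |
| 34/40 (85%) | 72.5% | 70.2% to 94.3% |
| 37/40 (92.5%) | 81.7% | not needed here |
| 38/40 (95%) | 85.1% | 83.1% to 99.4% |

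The one-sided 90% lower bound at 31/40 is 66.8%. The bare verdict of a pass therefore excludes, at one-sided 10%, only rates below about 66.8%. A higher count supports more, but the count and its interval carry that evidence and the verdict does not.

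**5. Other n.** The cap alone does not fix a cut-off. At n = 40, k = 30 gives 97.0% and breaks it, while every k from 31 (93.3%) to 40 (0.15%) meets it. Read as the smallest k that meets the cap, the rule returns 31 at n = 40. For n = 36 to 48 (36 is an assumed lower end) that reading gives cut-offs from 30/39 = 76.9% to 38/48 = 79.2% observed, with rejection at the boundary between 89.4% and 94.3%. The mismatch carries over.

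**6. A real test of the stated H0.** At an assumed one-sided 5% and n = 40, the smallest k with P(X ≥ k | 40, 0.85) ≤ 0.05 is 38 (size 0.0486; k = 37 gives 0.1302).

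**The case against.** The strongest reply is that nothing is hidden. The plan prints both operating points directly after the rule, both are right, and its opening sentence speaks of passing. A careful reader can see that the rule separates 85% from about 67%. This stands, and it is why the cut-off can be kept. It does not rescue the hypothesis pair: the two printed points leave out the range between them, where H0 is true and the rule often rejects it.

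Second, p = 0.85 belongs to H1 as written, so calling 93.3% power is formally allowed and the type I error only approaches it. This also stands, but a reader is not told that the same number limits the false-positive rate.

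Third, the aim to keep similar power characteristics rules out most cut-offs that the cap alone permits. That is fair, and it favours the smallest-k reading. The wording should say so.

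Fourth, the earlier App 1.0 study in Section 1.0 (45 subjects) reported 95% success with syncing and displays, so true rates of 75% to 80% may be unlikely. This lowers the likely practical impact for those features. It says nothing about the expanded Smart Reminders and does not repair the logic.

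Fifth, 31/40 is the rule for the reversed pair, H0: p ≥ 85%, rejected at 30 or fewer, with type I error 1 − 0.9328 = 6.7%. That is correct, and it confirms the concern: on that reading a pass means only that success was not shown to be below 85%.

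**Conclusion.** The concern holds and should be fixed before the primary result is reported. The arithmetic in Section 11.0 is sound. The stated hypotheses, the cut-off and the conclusion do not fit together. As a test of H0: p < 85%, the rule has a limiting type I error of 93.3% per statement and rejects a true H0 73.2% of the time at p = 80%. The figures rest on independent responses with a common success probability within a statement, and on n = 40 unless another n is given. The one-sided 5% level used for comparison, the true rates in the power figures and the lower end n = 36 are assumptions, because the plan gives none of them.

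**What to change.** **Recommended: keep 31/40 and change the wording and reporting.**

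1. In Section 11.0, replace the test of H0: p < 85% by an acceptance rule with stated operating characteristics: 93.3% pass at p = 85% and about 10% pass at p = 66.8%. Call 93.3% the pass probability at 85%.
2. If a null hypothesis is kept, state it as p ≤ about 66.8% at one-sided 10%, for n = 40 only.
3. For other n, define the cut-off as the smallest k with P(X ≥ k | n, 0.85) ≤ 95% and print the table below. It is needed per statement, since no-opinion answers and hardware or software failures leave the denominator ("will not be included in the numerator/denominator for calculating percentage of user success").
4. State that a pass does not demonstrate success of at least 85%.
5. Report an exact 95% confidence interval for each of statements 1, 8, 9 and 42 beside the 85% goal, and cross-reference this at the goal text in Sections 2.0 and 3.0.

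| n | k | Pass at p = 85% | p with 10% pass chance |
|---|---|---|---|
| 36 | 28 | 92.0% | 66.4% |
| 37 | 29 | 90.8% | 67.3% |
| 38 | 30 | 89.4% | 68.1% |
| 39 | 30 | 94.2% | 66.0% |
| 40 | 31 | 93.3% | 66.8% |
| 41 | 32 | 92.3% | 67.6% |
| 42 | 33 | 91.1% | 68.3% |
| 43 | 34 | 89.9% | 69.0% |
| 44 | 34 | 94.3% | 67.2% |
| 45 | 35 | 93.5% | 67.8% |
| 46 | 36 | 92.5% | 68.5% |
| 47 | 37 | 91.5% | 69.1% |
| 48 | 38 | 90.4% | 69.7% |

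The cost is editing and one table, with no extra subjects. The price is a weaker stated claim.

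**Alternative, a real trade-off and not recommended here:** keep H0: p < 85%, state an alpha, take the cut-off from it for the actual n, and state the power. At one-sided 5% and n = 40 the cut-off is 38/40, with power per statement of 22.3%, 67.7% and 95.4% at assumed true rates of 90%, 95% and 98%. Power of 80% at a true 95% is first reached at n = 59 (55/59, size 4.7%, power 82.8%). It is lost again at n = 63 to 67 and holds from n = 68. All of these exceed the planned enrolment of about 48.
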